1. In a sample of patients with POAG who have been on treatment with IOP lowering eye drops for at least three months, the frequency of signs of OSD, defined as hyperosmolarity, reduced NIKBUT, ocular surface staining, or reduced Schirmer 1 test, is different in patients with self-reported poor compliance, defined as single dose skipped or forgotten more than once a week (Robin & Grover, 2011), compared with patients with good self-reported compliance.
2. In a sample of patients with POAG who have been on treatment with IOP lowering eye drops for at least three months, the frequency of symptoms of OSD, defined as OSDI index ≥ 13 or SPEED II values >5 , is different in patients with self-reported poor compliance, defined as single dose skipped or forgotten more than once a week, compared with patients with good self-reported compliance.

3. In a sample of patients with POAG who have been on treatment with IOP lowering eye drops for at least three months, the frequency of signs of OSD, defined as hyperosmolarity, reduced NIKBUT, ocular surface staining, or reduced Schirmer 1 test, is different in patients with self-reported poor compliance, defined as single dose skipped or forgotten more than once a week, compared with patients with good self-reported compliance, when adjusted for preservatives, pharmacological substance, and duration of treatment.
4. In a sample of patients with POAG who have been on treatment with IOP lowering eye drops for at least three months, the frequency of symptoms of OSD, defined as OSDI index ≥ 13 or SPEED II values >5 , is different in patients with self-reported poor compliance, defined as single dose skipped or forgotten more than once a week, compared with patients with good self-reported compliance, when adjusted for preservatives, pharmacological substance, and duration of treatment.

The results are expected to improve the understanding of the connection between glaucoma treatment with IOP-lowering eye drops and ocular surface disease. Acknowledgment of the problem may help to individualize treatment options for patients in agreement with personalized medicine. This could consequentially lead to the general improvement of patient life quality and treatment compliance that could also positively affect glaucoma treatment outcomes.

Study design:

This is a cross-sectional study with six months prospective data collection.

Study sample:

The target population is patients on topical treatment for POAG.

Study population:

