Ocular surface staining (OSS) or superficial punctate staining is an inflammation marker presented as fine, scattered, punctate corneal epithelial loss or damage. Operationally, OSS is defined as a punctate staining pattern on the ocular surface that can be observed with slit-lamp biomicroscopy when the tear film is tinted with fluorescein sodium (MINIMS® Fluorescein Sodium 2%, Bausch&Lomb) and using a yellow filter (HUVITZ Microscope Slit-lamp HS-7000) and cobalt blue light. Evaluation of corneal staining is based on the Oxford schema (Bron, Evans, & Smith, 2003), which is used to estimate surface damage in dry eyes. Staining is subjectively assessed and graded in 0.5 steps on an ordinal scale using a clinical grading scale that ranges from 0 (absent) to 5 (severe) for the right and the left eye.

Meibum quality is defined as the degree of viscosity of the oil secreted from the Meibomian glands. Operationally, meibum quality is defined as the subjective assessment of the content of the meibomian glands by applying moderate digital pressure on each of the eight glands of the central third of the lower lid with a flat, perpendicular surface like index finger or Q-tip for 10 seconds. Properties of the expressed content of the glands are evaluated and registered in whole numbers on the ordinal scale from 0 to 3 (0=clear meibum; 1=cloudy meibum; 2=cloudy with debris (granular); 3=thick, like toothpaste) for each of the eight glands (Nichols et al., 2011) for the right and the left eye.

Meibum expressibility is defined as a combination of the viscosity and the integrity of the channels and orifices that make up for expressibility. Operationally meibum expressibility is defined as an ability to express the content of the meibomian glands in five central glands in the lower eyelid by applying moderate digital pressure on the glands. Evaluation of the meibum expressibility is performed simultaneously with an evaluation of the Meibum quality. Expressibility is recorded in whole numbers on

the ordinal scale from 0 to 3 (0=all glands expressible, 1=3-4 expressible, 2= 1-2 expressible, 3=non expressible) (Nichols et al., 2011).

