Subjects included in this study will undergo a comprehensive tear film evaluation on both eyes. All examinations will be performed by an experienced observer ([name]) in the fixed order from the least to the most invasive one. Firstly, **OSD-related disability (OSDI)** (Appendix 2), and **The nature of the symptoms (SPEED II)** (Appendix 3) will be examined by means of questionnaires. The patient will be given approximately 5 minutes to complete the questioners. The examiner will be in the room with the patient and will provide only a general explanation. The examiner will avoid interpreting or rephrasing the questions. The OSDI questioner has shown good specificity (0.83) and moderate sensitivity (0.60) when differentiating between dry eye disease patients and healthy patients (Schiffman et al., 2000). The sensitivity and specificity for the SPEED II questioner are 0.90 and 0.80 (Ngo et al., 2013). Thereafter, clinical examinations will be performed on the right eye followed by the left eye in this order: **Tear film osmolarity, Non-invasive Keratograph tear break-up time (NIK BUT), Bulbar redness, Tear Meniscus Height, Tear production (Schirmer 1 test), Ocular surface staining (OSS), Meibum quality, Meibum expressibility, Corneal sensitivity, Meibomian gland dropout.** **Tear film osmolarity** will be measured with The TearLab Osmolarity System by TearLab Corporation that has a precision (CV) of 1,5% with a standard deviation (Stdev) of 5.0 mOsm/L and accuracy of $r^2=0,95$. Tear collection will be performed at the lateral (temporal) extent of the eyelid, and the test card should touch the lower temporal tear meniscus. **Non-invasive Keratograph tear break-up time (NIK BUT), Bulbar redness, and Tear Meniscus Height (TMH)** will be measured with The Oculus Keratograph 5M by OCULUS, Inc. The patient will be instructed to place head correctly in the chinrest, and when the Keratograph is aligned with the patient's face, the patient will be instructed to blink twice. After the second blink, the measurement of the NIK BUT will automatically begin. The patient will be encouraged to keep their eyes open as long as possible without blinking. The

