measurement is automatically stopped by the device if the patient moves or blinks. **Bulbar redness** will be measured and graded automatically and objectively by taking a picture with the Oculus Keratograph 5M. Similarly, **Tear Meniscus Height (TMH)** will be measured objectively from the picture taken with Oculus Keratograph 5M that has an integrated ruler and various magnification options. Following, **Schirmer 1 test** will be performed without anesthetics. The free end of the non-toxic calibrated filter paper will be placed in the temporal part of the lower eyelid of both eyes, and the patient will be asked to hold the eyes gently closed for 5 minutes. At the end of the 5-minute interval, the paper strips will be removed from each lower eyelid, and the amount of wetting of the paper will be noted. Slit-lamp examination of the anterior segment will be performed in order to evaluate **Ocular surface staining (OSS)**. A quantified 5 µl of 2% Fluorescein sodium will be instilled into each conjunctival sac with a micro-pipette (using a sterile tip), and then observation will be done with a slit-lamp using a yellow filter and cobalt blue light. **Meibum quality** and **Meibum expressibility** will be also evaluated during the slit lamp exam. Meibum quality will be assessed in each of the eight glands of the central third of the lower lid by applying pressure on the eyelid with a Q-tip. It will be estimated and graded on a scale from 0 to 3 for each gland: 0=clear, 1= cloudy, 2= cloudy with debris (granular), and 3= thick, like toothpaste (total score range, 0–24) (Nichols et al., 2011). **Meibum expressibility** will be assessed in the five central glands in the lower lid by applying pressure on the lid with a Q-tip. It will be estimated on a scale from 0-3 (0= all glands expressible; 1=3-4 glands expressible; 2= 1-2 glands expressible; 3=no glands expressible) according to the number of glands expressible (Nichols et al., 2011). **Cochet – Bonnet Aesthesiometer** will be used to measure corneal sensitivity. Fine nylon filament, the length of which can be adjusted (60 mm to 5 mm), will be used to apply different intensities of stimuli on the corneal surface. The shortest length of the filament that the patient reacts will be noted. **Meibomian gland dropout (Meibography)** will be measured by taking infrared photos of the upper and lower eyelid with Oculus Keratograph 5M with minimal discomfort to the patient. Gland tissues will be made visible by everting the upper and lower eyelids with a Q-tip and using Meibo-Scan. The degree of Meibomian dropout will be scored and noted for all four eyelids. Finally, **Self-reported compliance** will be examined by means of simple interview question of how often one may skip a dose (Appendix 4). Information's about age, gender, duration of the treatment, the active pharmacological substance, and the preservatives in the topical IOP-lowering medication will be collected from the patient journals.

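### Compliance is asked orally after every ocular surface outcome is recorded, apparently by an observer who knows the findings, so its misclassification could depend on the signs (mainly secondary hypotheses 1 and 3)

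*Protocol*

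**What the plan says.** The secondary hypotheses (Protocol, Research objectives and significance) ask whether the frequency of signs (1 and 3) or symptoms (2 and 4) "is different in patients with self-reported poor compliance, defined as single dose skipped or forgotten more than once a week", compared with good compliance. Hypotheses 3 and 4 adjust for preservatives, substance and treatment duration.

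Under Predictor variables, the only source for compliance is one interview question with four frequency categories, from less than once or twice a month to more than once a week. No objective check is described.

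Methods: Measurements fixes the procedure:

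- "All examinations will be performed by an experienced observer", and the sequence runs "in the fixed order from the least to the most invasive one".
- OSDI and SPEED II come first and are completed by the patient, with the examiner present but giving no more than a general explanation. A further rule applies to these two questionnaires: "The examiner will avoid interpreting or rephrasing the questions".
- Ten clinical tests follow, from osmolarity to meibography. They include ocular surface staining, on which Outcome variables says: "Staining is subjectively assessed and graded in 0.5 steps on an ordinal scale".
- Compliance comes last and "will be examined by means of simple interview question of how often one may skip a dose (Appendix 4".

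The Analyses section describes Appendix 4 as the data registration form to which study data are transferred.

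**The concern.** When an exposure is ascertained after the outcome, by someone who knows the outcome, its errors may depend on the outcome. There are two routes here. The observer may ask, press or code differently after seeing a stained or dry eye. The patient may answer differently after an examination that has drawn attention to the eyes. The patients attend this clinic for glaucoma follow-up, which gives a plausible motive to under-report missed doses in any case. The question is whether the under-reporting differs by ocular surface status.

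If it does, the misclassification is differential and can move the odds ratio either way. Adjustment for preservatives, substance and duration does not touch it, and no later analysis can recover the true answers. The Introduction says it is unclear whether non-adherence is related to ocular surface disease. The secondary objective is meant to inform that question, so the ascertainment of compliance should not depend on the eye findings.

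This is a matter of data collection that the protocol itself fixes. It is not a detail that a statistical analysis plan could supply later.

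**Working it through.** **1. Order and safeguards, side by side**

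| Item | When | How obtained | Stated safeguard |
|---|---|---|---|
| OSDI, SPEED II | First | Completed by the patient, examiner in the room | No interpreting or rephrasing |
| Ten clinical tests | Middle | The one observer | Fixed order |
| Compliance | Last | Oral question | None stated |

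The ordering rule, least to most invasive, does not explain why a single question comes last.

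**2. Formula**

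The protocol gives no effect size, power or error rate for this comparison, so there is no figure to reproduce. What follows is illustration. Let p be the true proportion of poor compliers, equal with and without signs, so that the true odds ratio is 1. Let s1 and s0 be the probabilities that a truly poor complier is recorded as poor when signs are present and absent. Assume that good compliers are always recorded as good. Then

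observed OR = [p·s1 / (1 − p·s1)] ÷ [p·s0 / (1 − p·s0)].

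If s1 = s0, the two terms are equal and the observed OR is 1.00 for any p.

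**3. Worked example**

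The protocol's target is 30 subjects. The other inputs are assumed: 10 are truly poor compliers, half of each group has signs, and disclosure is 90% with signs and 60% without.

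- Truly poor: 5 with signs, 5 without. Truly good: 10 and 10.
- Recorded as poor: 5 × 0.9 = 4.5 with signs; 5 × 0.6 = 3.0 without.
- Recorded as good: 15 − 4.5 = 10.5 with signs; 15 − 3.0 = 12.0 without.
- Observed OR = (4.5 × 12.0) / (3.0 × 10.5) = 54 / 31.5 = 1.71.
- Disclosure reversed: 31.5 / 54 = 0.58.

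**4. Across the protocol's own range of non-adherence**

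The Introduction cites 23% to 59% non-adherence. Using that range for p is an assumption, because the protocol's definition of poor compliance need not match the one behind the cited range. All disclosure rates are also assumed.

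| Disclosure with / without signs | p = 0.23 | p = 0.41 | p = 0.59 |
|---|---|---|---|
| Equal (0.8/0.8 or 0.5/0.5) | 1.00 | 1.00 | 1.00 |
| 0.7 / 0.8 | 0.85 | 0.82 | 0.79 |
| 0.5 / 0.8 | 0.58 | 0.53 | 0.47 |
| 0.8 / 0.5 | 1.74 | 1.89 | 2.14 |
| 0.9 / 0.6 | 1.63 | 1.79 | 2.07 |

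**5. Bias against sampling error**

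For the cells in step 3, the standard error of log OR is √(1/4.5 + 1/3 + 1/10.5 + 1/12) = √0.734 = 0.86. The bias on that scale is ln 1.71 = 0.54, less than one standard error. The 95% interval around 1.71 is exp(0.54 ± 1.96 × 0.86), about 0.32 to 9.2.

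Take 30 subjects, ocular surface disease in 22% to 78% (the Introduction's range), p of 0.23 or 0.59 and a disclosure gap of 0.5 against 0.8 in either direction. A two-sided 5% test (sidedness is assumed) would then be nominally significant in about 4% to 16% of studies. This uses a normal approximation, which is rough because only about 4 to 13 patients would be recorded as poor compliers.

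**The case against.** The strongest reply is that asking last has a merit. Staining is graded subjectively and is one of the four sign criteria, and under the present order it is graded without knowledge of compliance. Moving the oral question to the start, with the same examiner asking, would exchange one bias for another. That stands against merely moving the question. It does not stand against a self-completed item that the examiner cannot see until grading is finished, which keeps this merit and removes the other problem.

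Several narrower objections also hold:

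- A reader might infer that the protocol has the grading examiner ask the question. It does not say so outright. The inference rests on one observer performing all examinations, on compliance being described as examined, and on no one else being named. Nor does it say that the examiner reads the symptom questionnaires, only that the examiner is present.
- Appendix 4 is not available here, so a script cannot be ruled out. Four closed categories also limit the room for probing. But the protocol describes the mode as an interview and the appendix as a data registration form, which points to staff recording the answer.
- Osmolarity, break-up time and Schirmer are device or strip readings, and nothing says that results are told to the patient before the question. This weakens the route through the patient. The route through the observer needs only that the observer knows the findings.
- A reader might infer that all four secondary hypotheses are affected alike. Symptoms are self-completed before any clinical test, so the signs seen do not act directly on hypotheses 2 and 4. What remains there is that the patient has just reported symptoms with the examiner present, and relocating the item would not remove that.

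**Conclusion.** The concern holds in a limited form. The compliance exposure is obtained orally after all outcomes are recorded, apparently by someone who knows them, and no masking or self-completion is stated. Differential misclassification is therefore possible, mainly in secondary hypotheses 1 and 3 and only weakly in 2 and 4.

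The documents give neither direction nor size. The odds ratios of about 1.7 and 0.6, and about 0.8 for a small gap, rest wholly on assumed disclosure rates. A reader might infer that the study is likely to report a false association. The figures do not support that: at 30 patients the assumed bias is less than one standard error, and nominal significance would be uncommon. The harm is a distorted estimate that later analysis cannot correct.

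This is an improvable design choice for a secondary objective, not a contradiction in the protocol. It is worth changing because it cannot be repaired after collection and costs very little.

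**What to change.** In Methods: Measurements, replace the end-of-visit interview with a self-completed item:

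- The patient ticks one of the four categories already listed under Predictor variables, at the same sitting as OSDI and SPEED II and before any clinical test.
- The sheet carries the study ID only and stays closed to the examiner until both eyes are graded, so that staining is still graded without knowledge of compliance.
- Predictor variables and Appendix 4 are aligned with this wording.

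The cost is about one line of text and one item moved to the questionnaire sheet, with no added staff or visit. The downside is that completeness can be checked only after grading. The change helps only patients seen after it is made.

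Two limitations remain and should be stated: general under-reporting of missed doses at the patient's own clinic, and correlation between a patient's own symptom and compliance reports, which bears on hypotheses 2 and 4.

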This study is a sub-study of an “Ocular Surface and glaucoma. A randomized study of IOP reducing eye drops versus surgical intervention” study (REK no. 253485). Invited to participate in the study are men and women between 50 and 75 years of age with early POAG, diagnosed in agreement with the European guidelines for glaucoma diagnoses and staging of the disease, with MD loss of less than 5 dB on visual fields and with a clinically significant cataract eligible for surgery, who come for a routine glaucoma follow-up examination and a presurgical assessment for cataract extraction at the ophthalmology practice of Ifocus Øyeklinikk in Haugesund, Norway, in the period between August 2021 and February 2022.

Exclusion criteria:

- Recent changes (<3 months) in the treatment with topical IOP-lowering medications (i.e., active pharmacological substance, dosage, preservatives) based on the patient medical journals.
- Use of more than one IOP-lowering eyedrops with different active pharmacological substances based on the patient medical journals.
- Self-reported OSD comorbidity defined as an autoimmune or inflammatory disease, such as Sjogren’s syndrome or Rheumatoid Arthritis (RA), or any other systemic disease that can directly affect the ocular surface.
- Conditions that may confound the results of the study:
 - Self-reported acute or chronic diseases such as connective tissue disease, clinically significant atopic disease, diabetes type 1 and 2, immunocompromised, or any other such condition.
 - Manifest corneal disease, dystrophy, or scarring based on the clinical exam.
 - Corneal ectasia based on the clinical exam.
 - Lid deformities based on the clinical exam.

- Recent intra- or extra-ocular surgery based on the patient medical journals.
- Previous refractive procedures like LASIK, LASEK, or radial keratotomy based on the patient medical journals.
- A previous corneal transplant, DSAEK, lamellar keratoplasty, or similar procedure based on the patient medical journals.

Recruitment:

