Recruitment of subjects will take place in the ophthalmologic practice of Ifocus Øyeklinikk in Haugesund, Norway. This study is a sub-study of an “Ocular Surface and glaucoma. A randomized study of IOP reducing eye drops versus surgical intervention” study (REK no. 253485), and the participants in this study will be recruited from subjects that have given their consent to participate in the main study. Patients who come for follow-up glaucoma controls with visual field examination in our clinic and meet all criteria for inclusion will be invited to participate in the study. Eligible patients will be given oral and written information about the study together with a consent form (Appendix 1). The recruited patients’ names will be replaced with unique randomized three-digit ID numbers to ensure the anonymity of the participants. The key list that links patients’ names with ID numbers will be deleted five years after the completion of the study. The aim is to recruit 30 subjects (60 eyes), which is a feasible number of subjects to perform a full ocular surface assessment on in the chosen timeframe of six months.

Variables:

Outcome variables:

OSD-related disability (The Ocular Surface Disease Index (OSDI)) is defined as an impairment caused by OSD that makes it more difficult for an individual to perform daily activities. Operationally, it is defined as the self-reported frequency of ocular symptoms (3 items), visual function (6 items), and environmental triggers (3 items) measured by means of The Ocular Surface Disease Index (Schiffman, Christianson, Jacobsen, Hirsch, & Reis, 2000), which is a validated questionnaire that has been proven to accurately differentiate between normal, mild to moderate, and severe dry eye disease. It measures the frequency of symptoms with one week recall period. The OSDI is registered in whole numbers on a numerical scale from 0 (0=no disability) to 100 (100=complete disability).

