Active pharmacological substance is an ingredient used in a finished pharmaceutical product, intended to provide pharmacological activity or to otherwise have a direct effect in the diagnosis, cure, treatment, or prevention of disease. Operationally, the active pharmacological substance is defined as any of the following substances in the specification of the prescribed eye drops during the period of 3 months before inclusion into the study: prostaglandin analogs, beta-blocker, carbohydrase inhibitor, or alfa-2-agonist. The active pharmacological substance used by the patients will be known from the patient history and will be noted on a nominal scale (1= prostaglandin analogs, 2=beta-blocker, 3=carbohydrase inhibitor, 4= alfa-2-agonist).

The duration of the treatment is defined as the period in which the patient has been treated with the same pharmacological substance. Operationally, it is defined as information about the duration of the treatment collected from the medical records and registered on a numerical scale with the whole number of months of use.

Self-reported compliance is defined as an act complying or adhering to requirements (prescribed treatment). Operationally, it is defined as self-reported adherence to taking drops in agreement with the prescription measured by means of a simple interview question of how often one may skip a dose (0: Less than once or twice a month; 1: Once or twice a month; 2: Approximately once a week; 3: More than once a week). It will be registered on an ordinal scale.

Other variables:

Age will be registered as the whole number of years on a numerical scale.

Sex will be registered as female=1 and male=0 on a dichotomous scale.

Methods:

Recruitment:

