
Analyses:

The results of the comprehensive tear film evaluation will be recorded in the patient journal system (Infodoc Plenario) used at the Ifocus Øyeklinikk, Haugesund, Norway. The data collected with the Oculus Keratograph 5M by OCULUS, Inc. will be stored in a separate database called Oculus Patient Data Management. Once measurements are performed, data related to the study will be transferred from the patient journal to a data registration form (Appendix 4). The names of the patients will be replaced with ID numbers. All data will be transferred to and organized in a database (Excel, Microsoft Inc.). To identify empty cells or unrealistic values, an algorithm in Excel will flag the cells in question. A quality-assured version of the database will constitute the basis for statistical analyses. For variables measured on a numerical scale, these summaries will include the sample size, as well as the mean, standard deviation, median, minimum, and maximum. For variables measured on a categorical scale, summaries will provide the number and percentage of subjects who provided each score. Preliminary considerations of the data will include the investigation as to whether any transformation (i.e., logarithmic) should be applied prior to the statistical analyses. For categorical data, the sparseness of the data across categories will be considered, and the combination of categories prior to statistical analysis will be applied where deemed appropriate. For variables measured on a continuous scale, the statistical significance of the difference

between groups will be investigated using an Analysis of Variance (ANOVA) with appropriate post-hoc testing. For variables measured on an ordinal categorical scale, the Kruskal-Wallis signed-rank test will be employed. Questionnaire data will be analyzed using current standards. The statistical analyses will be performed using SPSS version 24. All statistical tests of hypotheses will employ a level of significance of $\alpha=0.05$. Odds ratios with 95% confidence intervals may also be used.

Project management and organization:

Principal investigator: [name]

Project manager: [name]

Resources, equipment, and physical facilities:

All equipment is available in the ophthalmic practice Ifocus Øyeklinikk in Haugesund, Norway, where the study will take place:

- The TearLab Osmolality System by TearLab Corporations.
- The Oculus Keratograph 5M by OCULUS, Inc.

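### With 30 patients over four drug classes, a chi-square Kruskal-Wallis test may miss its 5% level in either direction; permutation p-values are a cheap remedy, and the test name needs correcting

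*Protocol*

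**What the plan says.** The protocol's Analyses section fixes the test, the software and the level:

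- "For variables measured on an ordinal categorical scale, the Kruskal-Wallis signed-rank test will be employed".
- "The statistical analyses will be performed using SPSS version 24".
- "All statistical tests of hypotheses will employ a level of significance of" 0.05.

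It does not say whether p-values are asymptotic, exact or Monte Carlo. On thin data it says that "the sparseness of the data across categories will be considered" and that categories may be combined at discretion.

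The predictor has four nominal levels (Predictor variables): "1= prostaglandin analogs, 2=beta-blocker, 3=carbohydrase inhibitor, 4= alfa-2-agonist". The exclusion criteria remove patients on several substances ("Use of more than one IOP-lowering eyedrops with different active pharmacological substances based on the patient medical journals"), so each patient falls in one class. The Recruitment section sets the size on feasibility: "The aim is to recruit 30 subjects (60 eyes), which is a feasible number of subjects". No expected or minimum class size appears anywhere.

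Under Outcome variables, the ordinal scales are staining (0 to 5 in half steps), meibum quality (0 to 3 per gland), meibum expressibility (0 to 3) and gland dropout (0 to 4).

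**The concern.** Four classes in 30 patients average 30/4 = 7.5. Patients come from routine attendance at one clinic without stratification, so some classes could be very small. The chi-square distribution is a large-sample reference for the Kruskal-Wallis statistic and can be poor when several groups hold one to three patients, or when most patients share one grade. The test would then not have the stated 5% level. In one direction real differences between substances are missed in a sample that is already small. In the other, false positives exceed what the protocol promises.

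The test name is also wrong. Kruskal-Wallis compares independent groups; a signed-rank test is for paired data. The quoted sentence merges the two.

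**Working it through.** **Plan's own figure.** There is no power or sample-size calculation to reproduce. The only figure to test is the 0.05 level.

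**Inputs from the protocol.** N = 30, four mutually exclusive classes, α = 0.05.

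**Assumed inputs.** Class splits, grade distributions, one value per patient, and chi-square p-values.

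**Statistic.** With midranks r, rank sums R_g and class sizes n_g:

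H = [Σ R_g²/n_g − N(N+1)²/4] / v, where v = Σ(r − (N+1)/2)²/(N−1).

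The asymptotic test rejects when H exceeds the 0.95 quantile of chi-square on 3 df, 7.815.

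**Hand check of the mechanism: split 27/1/1/1, no ties.** Here v = [30 × (30² − 1)/12]/29 = 2247.5/29 = 77.5. If the three single patients hold ranks 30, 29 and 1, their deviations from 15.5 are 14.5, 13.5 and −14.5. The between-class sum is 210.25 + 182.25 + 210.25 + 13.5²/27 = 609.5, so H = 609.5/77.5 = 7.86, just above the cut-off. Ranks {1, 2, 30}, {28, 29, 30} and {1, 2, 3} give the same H. The next largest sum is about 582.5, so H = 7.52, which is not significant. Only 4 of the C(30,3) = 4060 rank sets reject: a true level of 4/4060 = 0.1%, matching the simulated 0.10%.

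**True level of the chi-square version under the null** (40,000 runs per cell; simulation error about √(0.05 × 0.95/40,000) = 0.1 point):

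| Split | Untied or moderately tied | About 90% in lowest grade |
|---|---|---|
| 8/8/7/7 | 4.3–4.4% | 1.9% |
| 15/7/5/3 | 3.8–4.0% | 4.7% |
| 20/5/3/2 | 2.9–3.1% | 7.2% |
| 22/4/3/1 | 2.4–2.6% | 9.5% |
| 24/3/2/1 | 1.6–1.9% | 10.7% |
| 27/1/1/1 | below 0.2% | 14.8% |

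With about 75% in the lowest grade the level was 3.5–5.5% over all four-class splits tried, so the error changes sign as ties increase.

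**Chi-square against permutation p-values** (four-level outcome, 6,000 runs, 500 permutations each; error about 0.3 point for level and 0.6 for power). Power is for a 1-SD latent shift in the three smaller classes.

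| Split, ties | Level: chi-square v permutation | Power: chi-square v permutation |
|---|---|---|
| 20/5/3/2, moderate | 3.5% v 5.4% | 45% v 52% |
| 24/3/2/1, moderate | 1.7% v 4.8% | 28% v 42% |
| 20/5/3/2, heavy | 6.5% v 3.4% | 44% v 43% |
| 24/3/2/1, heavy | 10.3% v 3.6% | 49% v 41% |

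With an eight-grade outcome (2,500 runs, 999 permutations), power rose from 44% to 47% at 10/8/7/5 and from 50% to 55% at 15/8/5/2.

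So with moderate ties permutation recovers 7 to 14 points of power at the two small-class splits. With heavy ties it removes an inflated error rate, and the higher chi-square power there is bought with that inflation.

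**The case against.** *The protocol never says that large-sample p-values will be used.* This stands. A reader might infer from the named software and level that the plan commits to chi-square p-values, but no sentence says so. The choice may be made in a statistical analysis plan that is not shown, and silence on it is not an error. What remains is that the Analyses section already fixes test, software and level, and a better way to obtain the p-value at this sample size can be added there.

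*The class sizes are assumed.* This also stands. At near-balance with light or moderate ties the gain is a few points at most.

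*Sparse categories may be combined.* This could help. With the three smaller classes merged and ordinary chi-square p-values kept, the simulated level was 4.5–4.8%. Power was 66%, 70%, 65% and 51% at 10/8/7/5, 15/8/5/2, 20/6/3/1 and 24/3/2/1, against 47%, 55%, 54% and 42% for the four-class permutation test. But that alternative gives all three classes the same shift, which is what merging favours. Merging also gives up the four-class comparison, is discretionary in the protocol, and is not clearly meant for drug classes.

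*Three broader readings are tempting and not supported.*

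- That the test is always conservative: heavy ties can reverse the direction.
- That research question 3 as a whole is tested at the wrong level: main hypotheses 3 and 4 concern frequencies of dichotomous composites. Of their components only staining is ordinal; osmolarity, break-up time, Schirmer, OSDI and SPEED II are numerical.
- That the ANOVA needs the same remedy: its level was about 5% for normal data. It rose to 7.0% and 8.3% (20/6/3/1 and 24/3/2/1) only for untransformed lognormal data, and the protocol plans to consider a logarithmic transformation first.

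**Conclusion.** The point holds as a cheap improvement of minor severity. If chi-square p-values are used and some classes hold about one to three patients, the real level for ordinal outcomes is about 1.5–4% with light or moderate ties, with about 5–15 points of power lost. It is about 7–11%, and higher at the most extreme split, when some 90% of patients share the lowest grade. Splits more extreme than 24/3/2/1 fall below 1.5% when ties are light. Permutation p-values stayed close to or below 5% in the scenarios checked and leave the statistic and the four-class question unchanged. All of this rests on assumed splits and grade distributions and on one value per patient. The misnamed test is a definite error whatever the class sizes. Neither p-value method makes classes of one to three patients informative, and the lack of any power basis for 30 patients matters more.

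**What to change.** In the Analyses section:

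1. Correct the name to Kruskal-Wallis test, deleting *signed-rank*.
2. State that Kruskal-Wallis comparisons across substance classes use exact or Monte Carlo permutation p-values, for example 10,000 random reallocations of class labels. Reallocate among patients, not eyes, because both eyes of a patient share one drug class.

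No change to the ANOVA is needed on this account. The cost is one sentence and seconds of computing, with no new data. The downside is that it may need the SPSS exact-tests option or another package.
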